- 3) **Identify subgroups of AA non-daily smokers for whom the relative benefits of treatment might differ using novel Classification and Regression Tree (CART) modeling methods that can be directly implemented into clinical practice.**

B. Background and Significance

Smoking is associated with significant health burden in the US. Despite tobacco control efforts that have resulted in overall reductions in smoking prevalence, smoking is still the number one cause of

preventable disease and death in the U.S, killing nearly 445,000 Americans each year. Smoking is also a major contributor to chronic disease. For every one adult who dies from smoking, another 20 live with one or more tobacco-related chronic illnesses, including heart disease, cancer, chronic-obstructive lung disease, and stroke. The economic impact of smoking is staggering. Annually, cigarette smoking is responsible for an estimated \$96 billion in direct medical costs and \$97 billion in lost productivity.¹ At the employer-level each employee who smokes costs nearly \$6,000 more each year than their non-smoking counterpart, due mostly to more time off for sickness, frequent smoke breaks/lost productivity, and increased health care costs and pension benefits for smokers.² Few conditions impose a more significant health burden on the U.S population.

Smoking imposes a more significant burden on African Americans at lower levels of smoking.

The burden of smoking is not equally distributed across the population.³ While non-Hispanic African American (subsequently referred to as AA) adults smoke at rates that are slightly lower than non-Hispanic White adults (19.4% versus 20.6%) (subsequently referred to as White),⁴ they have disproportionately higher rates of tobacco-related disease and death. AAs have the highest incidence rates for all cancers combined, the highest overall cancer mortality rates compared to all other racial/ethnic groups, and have twice the rates of premature death attributable to cardiovascular disease.⁵ In addition, AA smokers have a 43-55% higher relative risk of smoking attributable lung cancer compared to Whites⁶ and are at higher risk for nearly all smoking-related chronic diseases.^{7,8}

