This study addresses each of the funders (PCORI) criteria for significance (noted in italicized and underlined text). Specifically, it addresses a critical gap in current knowledge, is novel, and responds directly to the call for guideline development efforts. To date, **no** fully powered randomized clinical trials have been conducted with non-daily smokers despite the fact that they represent 1 in 7 White and 1 in 4 AA smokers. This study will determine if NRT is effective for AA non-daily smokers. The program will be the first to examine treatment options for non-daily smokers and could directly contribute to the first evidence-based guidelines for treating the 9.7 million U.S. adult non-daily smokers for whom no guidelines currently exist. By providing the first-ever data on the efficacy of counseling alone versus counseling plus NRT, efficacy of patch versus gum versus lozenge, and clearer protocols for titrating NRT dose to address the unique smoking patterns of non-daily smokers, the

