study will not only inform evidence-based guidelines but also address the wide variations in practice patterns that suggest clinical uncertainty in treating non-daily smokers. The proposal has been identified as important by patient and clinician groups. Throughout the course of our ongoing smoking cessation programs at Swope Health Central, one of two recruitment sites for this study, a growing number of AA smokers were being excluded because of their non-daily smoking status, and we received countless requests for help from AA non-daily smokers. At the same time, providers expressed concern about the lack of evidence-based recommendations for treating non-daily smokers and the need for a quit smoking program to meet the demands of this growing patient population. The study is directly derived from these requests. Finally, the experience of our group, our previous success using research finding to change policy/practice, and integration of the CART decision tree (Aim 3) into electronic medical records will ensure that the findings, whether positive or negative, are disseminated quickly and affect changes in current practice. A distinct advantage of this proposal is that its ability to impact practice is not tied to finding group differences in the hypothesized directions (Aims 1, 2). Rather, independent of whether there is an overall difference between groups in treatment efficacy, our decision tree will identify subgroups for whom treatment efficacy differs. Some patients may benefit most from counseling only, others may benefit from counseling and nicotine patch, and others may benefit from counseling and gum or lozenge. Our decision tree will identify these subgroups, allow patients and providers to estimate an individual's chance of success given their treatment and select patient characteristics (e.g., gender, age, menthol versus non-menthol cigarettes, nicotine dependence, nicotine intake, polytobacco versus cigarette only use), and can be directly implemented into clinical practice.

C. Rationale

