To date, no studies have explored treatment options for non-daily smokers and, as a result, treatment guidelines are not available to guide patients or healthcare providers. The study will compare two treatments -- smoking cessation counseling alone versus counseling in combination with patients' choice of nicotine patch, gum, or lozenge -- on their effects on quitting smoking and reducing exposure to nicotine and cancer causing agents. Findings will identify which patients are most likely to benefit from each form of treatment (counseling, nicotine gum, patch, or lozenge) and will allow patients and providers to estimate their chances of success based on personal characteristics – for example, age, gender, level of smoking – and the treatment they chose. This study will determine if NRT is safe and effective for AA non-daily smokers. The program will be the first to examine treatment options for non-daily smokers and could directly contribute to the first evidence-based guidelines for treating the 9.7 million U.S. adult non-daily smokers for whom no guidelines currently exist.

[figure not shown]
II. RESEARCH PLAN AND DESIGN

A. Study Objectives

The objective of this study is to examine if NRT is an effective treatment option for AA non-daily smokers. Outcomes will be measured at weeks 12 and 26 and will include biologically confirmed smoking abstinence, nicotine intake, carcinogen exposure, days abstinent, NRT adherence and side effects.

B. Study Type and Design:

The proposed study is a randomized trial of 384 AA non-daily smokers randomized to receive either 5 sessions of smoking

Projected sample size by group using 2:1 randomization, whereby 67% are randomized to C+NRT and 33% are randomized to C

cessation counseling in combination with 12 weeks of nicotine patch, gum, or lozenge (C+NRT) or 5 sessions of smoking cessation counseling alone (C). We will use 2:1 randomization; for every patient randomized to C, two will be randomized to C+NRT (see Figure). The primary outcome is biologically-confirmed 7-day abstinence from smoking at 12 weeks. Patient- and provider-driven secondary outcomes include reductions in nicotine intake and carcinogen exposure, days abstinent, NRT adherence and side effects. Participants will be recruited from the University of Kansas Medical Center (KUMC) and Swope Health Central, a community-based primary care clinic in urban Kansas City that serves a predominately AA clientele.

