Specific Aim 3: Identify subgroups of AA non-daily smokers for whom the relative benefits of treatment might differ. We will employ a Classification and Regression Tree decision tree modeling on Week 12 verified smoking status (quit versus not quit) to identify subgroups of participants whose personal characteristics might impact the benefit of treatment. The resulting decision tree will allow smokers and their providers to estimate their individual chances of success given their choice of treatment. To maximize the utility of the decision tree, we solicited input from our Stakeholder Advisory Committee and Patient Advisory Panel and included the demographic, smoking, and treatment-related variables identified by them (see Measures and Time Points Table) for possible inclusion in the predictive model. The candidate variables, along with treatment assignment (C, C+NRT) will be entered into a recursive partitioning model as described by Brieman and Freidman using the RPART package in the R statistical software.⁴⁷ Specific methods related to building the tree (using appropriate splitting criteria and loss incorporation using the altered priors method), pruning the tree and handling missing data (using surrogate variables) will be deployed using the techniques described by Therneau et al.⁴⁸ Given the cessation rate expected and overall sample size, a validation subsampling scheme will not be feasible, thus we will utilize 10-fold cross-validation on the regression tree to assess its properties. Additionally, we will account for the uncertainty in tree classification by

generating a bootstrap sampling distribution of the predictive as described by Shalizi.⁴⁹ Modeling cessation was of greatest interest for our initial Patient and Stakeholder Advisory Panels, but other outcomes (reduction in nicotine or carcinogen exposure) could be modeled if our patients and stakeholders think that these additional models might be useful.

D. Subject Criteria (See Vulnerable Populations appendix, if applicable)

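### Aim 3 promises subgroups in which the benefit of C+NRT over C differs, but plans only a tree for quit status, with no arm contrast in any subgroup and with self-selected product among the candidates

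*Combined protocol and SAP*

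**What the plan says.** **The promise.** In section I.A, Aim 3 reads "Identify subgroups of AA non-daily smokers for whom the relative benefits of treatment might differ using novel", and goes on to name tree methods. The Significance part of section I.B is firmer. Whatever the overall result, "our decision tree will identify subgroups for whom treatment efficacy differs", and it foresees "integration of the CART decision tree (Aim 3) into electronic medical records". It also advertises data on the "efficacy of patch versus gum versus lozenge". The Rationale (section I.C) says the findings will show who gains most from counseling and from each NRT product.

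**The method.** Section II.C, Specific Aim 3, plans one classification tree on quit versus not quit at Week 12: "The candidate variables, along with treatment assignment (C, C+NRT) will be entered into a recursive partitioning model". A second stated use is to let smokers and providers "estimate their individual chances of success given their choice of treatment". Altered priors, pruning and surrogate splits are named and referred to a manual, without values. Ten-fold cross-validation and a bootstrap for classification uncertainty are planned.

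**The candidates.** The plan says it "included the demographic, smoking, and treatment-related variables identified by them" and points to the measures table. In section II.E that table lists, under covariates for Aims 1, 2 and 3, treatment assignment and, within C+NRT, the chosen product. The product is chosen after randomization, following a short trial of the products. Specific Aim 1 declines a statistical comparison of products because the choice is not random.

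**The concern.** Differing benefit means that the C versus C+NRT difference changes between subgroups. A tree for quitting is built to separate quitters from non-quitters, so its splits may reflect prognosis alone. Cross-validation and the bootstrap, as the plan words them, address prediction of quitting and not the arm difference.

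The tree is meant for electronic medical records whether the findings are positive or negative. Without an arm contrast in each subgroup, a prognostic group, or a group defined by the product people chose, can be read as a group that benefits more or less from NRT. Product raises a second problem: a split between products is not a randomized comparison, and Aim 1 already says so.

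**Working it through.** **Inputs from section II.C.** 128 in C and 256 in C+NRT; quit rates of 10% and 20-25%; losses to follow-up counted as smokers. Aim 3 has no power or precision figure of its own.

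**1. The plan's overall power reproduces.** Two-sided pooled chi-square, no continuity correction: power = Φ[(d − 1.96·SE0)/SE1]. For 10% vs 22.5%:
- d = 0.125 and the pooled rate is (12.8 + 57.6)/384 = 0.1833.
- SE0 = √(0.1833·0.8167·(1/128 + 1/256)) = 0.0419.
- SE1 = √(0.09/128 + 0.1744/256) = 0.0372.
- Power is 87.6% (stated 87%).

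The same formula gives 95.7% at 25% and 71.7% at 20% (stated 95% and 71%).

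**2. A split on quitting need not be a difference in benefit.** Suppose C quits at 5% and 15% in two equal halves, and C+NRT at 17.5% and 27.5%. Benefit is 12.5 points in both. Pooled 2:1, the halves quit at (5 + 2·17.5)/3 = 13.3% and (15 + 2·27.5)/3 = 23.3%, so a quit tree may split there. In 400 simulated unpruned trees of depth 3 per prior setting, the first split fell on this covariate in 22-24%, and treatment appeared nowhere in 25-33%.

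**3. The unstated priors or losses decide whether treatment shows.** If a missed quitter weighs w times a false quitter, a leaf with quit rate p is labelled quit when w > (1 − p)/p. Taken alone, a treatment split lowers misclassification cost only if the arms get different labels:
- C+NRT at 22.5%: w > 0.775/0.225 = 3.4 (4 at 20%; 3 at 25%).
- C at 10%: w < 0.90/0.10 = 9.
- Equal priors imply w = (384 − 70.4)/70.4 = 4.5, inside the range. Observed priors (w = 1) and losses of 2:1 or 3:1 fall outside it.

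Simulation agrees. Settings were rpart with Gini and default controls, 10-fold cross-validation, 15 baseline covariates (6 two-valued, 9 ten-level), 10% vs 22.5%, and uniform benefit. The share of patients given the same chance on C and C+NRT, under minimum-CV / one-standard-error (1-SE) pruning, was:
- Equal priors, inert covariates: 20/23%.
- Equal priors, three prognostic covariates: 59/65%.
- Observed priors, or 2:1 or 3:1 loss: 99-100%, because the tree hardly ever splits.

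**4. Product as a candidate.** Assumed: a *none* level in C, equal thirds in C+NRT, equally effective products, equal priors, inert covariates, minimum-CV pruning. Two sets of runs (300 and 400) had 25-27% and 29% of trees separating products. A split of *none* against all products is the randomized split under another name. Counting it, trees keeping the C versus C+NRT contrast fell from about 87% to 66-75%. If product were instead coded missing in C, surrogate splits would place C participants; the plan does not say which applies.

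**5. Precision of a subgroup contrast.** Half-width = 1.96·√(p2(1 − p2)/n2 + p1(1 − p1)/n1).
- Half the sample (128/64): 1.96·√(0.225·0.775/128 + 0.1·0.9/64) = 0.103, with 6.4 expected C quitters.
- A quarter (64/32): 0.146, with 3.2 expected C quitters.
- Difference in benefit between two halves detectable with 80% power: (1.96 + 0.84)·√2·0.0526 = 0.208. That exceeds the planned overall effect of 10-15 points.

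**6. Ordinary leaf intervals would mislead.** Under uniform benefit with inert covariates and equal priors, 60/42% of trees formed more than one covariate subgroup. In those trees the largest and smallest arm differences lay a median 34/17 points apart (truth 0), and ordinary 95% intervals covered the truth in 79/81% of leaves.

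**The case against.** **Treatment is in the tree and the aim is hedged.** Treatment is a named candidate, so where it splits, an arm difference can be read off the leaves. Aim 3 says benefits might differ, has no hypothesis, test or power claim, and concedes that a validation subsample is not feasible. The firm wording is in the Significance and Rationale parts. All this stands, and it supports an exploratory label. It does not supply a planned contrast, and a contrast that appears only if treatment happens to split is not one. The bootstrap's details lie in cited lecture notes outside the documents; as worded, it concerns prediction.

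**A reader might infer that a quit tree cannot find effect modifiers and must give way to an interaction search.** The documents do not support that. The tree suits the stated use of estimating chances of success. With equal priors, inert covariates and a matched false-subgroup rate, it found a modifier that also raises overall quitting more often than an interaction search (C 10% in both halves, C+NRT 10 vs 40%: 91/79% against 58/51%). It did worse when effects cancel (C to C+NRT: 5 to 25% in one half, 25 to 15% in the other): 19/9% against 94/91%. No section suggests which case applies, so an interaction analysis is optional.

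**A reader might also infer that product displaces randomized treatment in most trees.** Counted by variable name alone, use of treatment does drop to about 25-45%, depending partly on column order. That is largely a labelling effect, as step 4 shows.

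**Patients and stakeholders helped choose the variables.** Dropping product from the benefit tree removes an output they may want. That cost is real, but a descriptive summary keeps most of the information without suggesting a randomized comparison.

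**Conclusion.** The gap between promise and plan stands on the text alone: no section plans a C versus C+NRT difference or interval in any subgroup. The conflict over product also stands on the text, since the measures table makes it an Aim 3 covariate and Aim 1 explains why products should not be compared statistically.

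The simulated sizes are illustrative. They rest on assumed priors, losses, covariate coding, prognostic effects and product shares, and the covariate set omits nicotine intake, which the Significance part names as a patient characteristic. Steps 4 and 6 use equal priors and would not carry over to settings where the tree hardly splits. Monte Carlo error is up to about 5 points with 400 runs and 6 with 300 (1.96·√(0.25/300) = 0.057).

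This should be corrected before analysis, because the tree is meant for clinical records. It does not touch the Aim 1 comparison.

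**What to change.** - **Section II.C, Specific Aim 3.** Keep the rpart tree for estimating chances of success. State its priors or losses and its pruning rule.
- **Add an arm contrast.** For each subgroup defined by the tree's covariate conditions, with treatment splits dropped (a leaf below a treatment split holds one arm only), report numbers, C and C+NRT quit rates, and their difference. Give a bootstrap interval that repeats tree building and pruning. State that any claim of differing benefit rests on these contrasts and not on the splits.
- **Specific Aim 3 and the section II.E measures table.** Exclude product from the benefit tree. Summarise quit rates by product descriptively within C+NRT, as Aim 1 already does.
- **Sections I.B and I.C.** Label Aim 3 exploratory, and soften the statements that subgroups will be identified and that product efficacy will be shown.
- **Optional.** A supplementary analysis aimed at treatment-by-covariate interaction, with a stated threshold.

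The cost is plan wording and modest extra analysis on the same data. The downsides should be stated: intervals of about ±10 points in a half-sample subgroup and ±15 in a quarter-sample, some leaves with few C participants (35/10% of simulated trees had a leaf with fewer than 10, under uniform benefit and inert covariates), and product-specific chances that are descriptive only.

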NRT (C+NRT). Participants randomized to C+NRT will be given their choice of nicotine gum, patch, or lozenge to try for 3 days each. After the 3 to 9-day trial period, they will select and receive a 12 week supply of the medication of their choice. Similar NRT choice trials have been used successfully by others.⁵² This patient-centered approach was informed by our Patient Advisory Panel, who preferred these medications because of cost and over the counter availability, and our Stakeholder Advisory Panel, who felt that this patient-centered approach emulated clinical practice and would broaden the implications of our study for informing evidence-based guidelines for treating tobacco dependence in AA non-daily smokers. Nicotine gum, patch, and lozenge are all highly effective first-line medications approved for the treatment of tobacco dependence that have been shown to double the rate of quitting compared to placebo.^{11,28} NRT dosing. One of the clinical implications of this study is to inform the development of NRT dosing guidelines for non-daily smokers. We will work hand-in-hand with our providers and quitline experts to ensure that the counseling and NRT dosing protocols can be easily implemented with non-daily smokers in clinical practice and through the national quitline, Alere. We draw on our decades of experience treating AA smokers, the well-established literature on nicotine metabolism among AA smokers, and expert consensus to derive NRT dosing guidelines. Urine cotinine levels from AA daily smokers are consistent with taking in the equivalent of 8-10 mg of nicotine per day.⁴⁰ Urinary cotinine data from our NDS pilot study indicate that AA non-daily smokers have an average daily intake of cotinine that is 61% that of daily smokers or equivalent to 5.5 mg of nicotine per day.³⁵ The goal of treatment with NRT is to replace most or all of the nicotine that would have been obtained from tobacco with nicotine from the replacement product. However, not all nicotine from NRT is absorbed into the system. For a 7 mg patch, approximately 5 mg of nicotine is absorbed.⁵³ Likewise, for each 2 mg gum or lozenge, only 1 mg of nicotine is absorbed.⁵⁴ Following from the absorption rates of these products and our preliminary data indicating that AA non-daily smokers are in need of at least 5.5 mg of replacement nicotine per day, participants choosing the patch will be started on one 7 mg patch/day and those choosing gum/lozenge will be started on six 2 mg pieces/day.

These doses represent a starting point. To enhance the ability of our findings to be translated into practice, counselors will educate participants about the relationship between cpd and NRT dosing and empower them to tailor use to be consistent with their smoking patterns, intensity of withdrawal and craving, and level of side effects. Participants will be taught that, if the NRT dose is adequate, they may still have urges during the day, but most of the time they will not feel strong physical cravings or discomfort. They will also be educated about side effects that may indicate a nicotine overdose (nausea, vomiting, cramps, dizziness) and the need for a dose reduction (i.e., fewer pieces of gum/lozenge per day, reduction from 24 to 16 or 12 hours per day that the patch is worn), as well as symptoms of withdrawal (e.g., irritability, restlessness, anxiety) and strong physical craving that may indicate the need for a dose increase (i.e., more pieces of gum/lozenge per day, increase to longer wear or a higher dose patch). Counselors will probe for smoking level, use of NRT (days used, amount used per day), side effects, symptoms of withdrawal and craving, and general experiences with the

medication during the week 1, 4, 6, 8, and 10 sessions and will provide guidance, as necessary, to ensure that the medication is working optimally for each participant. The PI and study physician will provide oversight on questions and issues that arise related to side effects, dose reductions and/or increases.

Overview of Major Study Events

		Enroll./ Baseline					EOT	Final Follow- Up
		Wk 0*	Wk 1	Wk 4	Wk 8	Wk 10	Wk 12*	Wk 26*
Screening/ Assessments	X	X		X	X		X	X
Intervention								
Counseling		X	X	X	X	X		
Medication Dispensing (C+NRT only)		X (3 to 9- day trial period)	X	X	X		X	

*in person; all other visits are by telephone; EOT=end of treatment

Procedures and Methods

An overview of major study events is provided in the adjoining table.

Initial Screening.

The initial screen will review inclusion/exclusion criteria. Those eligible will be scheduled to complete final eligibility screening within 14 days. All ineligible smokers will be referred to local resources.

Final Screening and Enrollment (Wk 0). Final eligibility screening will be conducted in person and will consist of a pregnancy test on women of childbearing age and obtaining informed consent.

Counseling Visits (Wks 0,1,4,8,10). Counseling sessions will be completed by phone at Wks 1,4, 8,10, and in person at Wk 0. The number of sessions is consistent with our previous studies where we have achieved visit completion rates of around 80%.^{45,55,56}

NRT Dispensing (Wks 0-1). Participants randomized to C+NRT will be given a trial supply of nicotine gum, patch, and lozenge and be instructed to try each for 3-days. After the 3 to 9-day trial period, they will select and be mailed a 4 week supply of the medication of their choice. They will receive refills of their selected medication at the Weeks 4 and 8 study visits.

Biological Sample Collection (Wk 0,12,26). Urine will be collected three times throughout the study for biochemical verification of cessation at Wk 12 and Wk 26, nicotine intake at Wks 0, 12, 26, and carcinogen exposure at Wks 0, 12, and 26. Additional details regarding each assay are provided in the Measures and Assessment Time Points table.

Retention. We have developed a system of reminders and compensation that have resulted in impressive retention rates in our previous clinical trials. Reminders. One week prior to each scheduled visit a reminder postcard noting the scheduled appointment date and time will be mailed to participants. In addition, participants will be called up to 6 times to remind them of their upcoming visit. A detailed tracking database, with an automated reminder system, will notify counselors of when to send postcards and complete reminder phone calls. Compensation. Participants will be given a \$40 electronically loaded gift card at Wks 0, 12 and a \$20 electronically loaded gift card at Wks 1, 4, 8, 10, 26 in appreciation for their time and participation.

Measures

Our selection of measures (see table) and the measurement time points have been driven by our patient and stakeholder advisory panels.

Measure and Assessment Time Points

Primary Scientific Outcome (Aim 1)
Smoking abstinence at Wk 12 (primary cessation outcome) and Wk 26 (secondary cessation outcome). Biochemically confirmed at Wk 12 using urine anabasine and anatabine, with the recommended cut-off of 2 ng/ml to differentiate smokers from non-smokers. ⁵⁰ These tobacco alkaloids are considered the gold standard for confirming abstinence when cotinine measurements are not valid – i.e., detectable levels of cotinine could reflect NRT use or smoking. ⁵⁰ Biochemically confirmed at Wk 26 using urinary cotinine, the proximate metabolite of nicotine, with the recommended cut-off of 50 ng/ml used to differentiate smokers from non-smokers. ⁵¹ Time Points: Wk 12, 26
Secondary Patient- and Provider-Derived Outcomes (Aim 2)
Nicotine intake (total nicotine equivalents/creatinine). Assessed by urine; quantified by examining the sum of four of the major nicotine metabolites (cotinine + cotinine-glucuronide + trans-3'-hydroxycotinine + 3HC-glucuronide) to creatinine ratio using procedures described by [name] (consultant). ⁵¹ Total nicotine equivalents/creatinine represents the current gold standard for estimating nicotine intake/exposure from tobacco. ⁵⁷ To ensure that nicotine metabolites detected at Wk 12 are a result of tobacco exposure and not NRT use, we will schedule the urine collection for 7 days after the last dose of NRT. This 7-day time frame is more than adequate given the 15-20 hour (3-4 day) elimination half-life of cotinine and accounts for the substantial individual variability in the rate of elimination of nicotine. ⁵⁸ Time Points: Wks 0,12,26
Carcinogen exposure [NNAL, PAH]. Assessed by urine; quantified by examining NNAL (4-(methylnitrosamino)-1-(3)pyridyl-1-butanol) and polycyclic aromatic hydrocarbons (PAH) and specifically, 1-hydroxypyrene (1-HOP), using procedures described by [name] (consultant). ⁴⁰ While there are >70 established carcinogens in tobacco, NNAL and PAH are widely considered to be among the most important causative agents in the development of lung and esophageal cancer ^{38,39,59} and reflect the current gold standard for estimating carcinogen exposure from tobacco products. Time Points: Wks 0,12,26
Days Abstinent. Cumulative number of days abstinent Time Points: Wks 1,4,8,10,12
NRT adherence. 3-day recall of NRT use (C+NRT only) -- i.e., pieces of gum, lozenge, or number of patches used in the last 3 Time Points: Wks 4,8,12
Side effects. Participants will be asked about symptoms commonly associated with quitting smoking and/or NRT (i.e., difficulty concentrating, irritability, skin rash, mouth/throat irritation, nausea, sleep disturbance, heart burn) Time Points: Wks 4,8,12
Covariates (Aims 1, 2 & 3)
Demographics. Includes gender, age, income, education level, marital status, and use of alcohol Time Point: Wk 0
Smoking history. Includes type of cigarette (menthol, non-menthol), days smoked per month, number of cigarettes smoked per day on days smoked, length of time smoking at current non-daily rate, age of smoking initiation, time to first cigarette of the day (nicotine dependence), use of cigarettes only or cigarettes in combination with alternative forms of tobacco (ATP; e.g., cigars, cigarillos), presence of other smokers in the home, and home smoking restrictions Time Point: Wk 0
Treatment. Includes treatment assignment (C, C+NRT) and, for those randomized to C+NRT, their choice of nicotine gum, lozenge, or patch.

Clearly indicate which procedures, tests, visits, etc., are parts of usual standard therapy and which are performed solely for research purposes.

All tests, procedures, and visits are being performed solely for research purposes and are not billable to insurance companies.

Describe the fate of any body component (blood, CSF, bone marrow, etc.) used in the study, emphasizing confidentiality of labeling of the sample and the sample's destruction or storage.

Samples will be labeled only with a unique study identification number and only members of [name] and [name]'s team will have access to the samples. Samples will be disposed of one month after the final report is sent out to the Principal Investigator, unless participants agree to have their urine stored for future testing.

F. Risk/benefit assessment:

Physical risk

Risks for participating in the study are primarily those related to the use of NRT for participants randomized to the C+NRT arm. The safety of NRT has been demonstrated in hundreds of studies spanning over 30 years of research, including studies of patients who are very low level smokers and nonsmokers. To minimize any possible risk, we will exclude any patients with unstable heart disease (i.e., unstable angina or AMI in the past 4 weeks) per the medical contraindications for NRT.

Nevertheless, NRT, particularly in continuing smokers, can be associated with nausea, jitteriness,

insomnia, and vivid dreams. To address these concerns, participants will receive written information and information from their counselor about how to manage any of these symptoms. They will be given advice on when they might need to reduce their nicotine dose (whether through decreasing smoking or decreasing NRT). We will track adverse events and review adverse events regularly (see data safety and monitoring plan below).

Psychological risk

Risks for participants in both treatment arms (C, C+NRT) also include those associated with the inconvenience of participation including answering surveys, providing urine, and participating in follow-up visits and assessments. To minimize the inconveniences associated with study participation we will review all data collection instruments and study procedures with our Patient Advisory Panel and our Stakeholder Advisory Committee. We will use their input to minimize the number of items in our instruments and improve the accessibility and convenience of our study procedures. We anticipate using several methods to enhance convenience to participants, including offering study visits in the evening and on weekends and offering patients a choice of where they will be seen (KUMC or Swope). Another risk is feeling pressured to be in the study, which we will track in order to monitor and will report this as an adverse event.

Social risk

None

Economic risk

None

Potential benefit of participating in the study

There are also no direct benefits to participating in this study except that researchers hope that the information from this research study may be useful in improving treatment for non-daily smokers.

G. Location where study will be performed:

The study will take place at Swope Health Central, [name], in Kansas, Missouri or at the KUMC CRU in Fairway, Kansas based on the preference of each participant. All data will be directly entered into an electronic data capture system (i.e., RedCap or CRIS), therefore minimizing the use of paper records. If paper records are generated, they will be stored in locked file cabinets at Swope. Only study staff will have access to the locked records at Swope and the secure online electronic data capture system.

H. Collaboration (with another institution, if applicable):

